7.1 Follow-up Procedures

Patients will be followed for safety assessments at post-operative day 1, and at visits 3, 4, and 5. Data collection will include routine treatment data, assessment of urinary obstruction requiring Foley catheter placement as well as signs or symptoms of infection requiring additional antibiotics or hospital admission felt to be directly related to the procedure.

8.0 Correlative/Special Studies

N/A

9.0 Safety and Effectiveness Assessments

9.1 Safety Assessments

Laboratory values obtained as part of the routine pre-surgical evaluation for prostate brachytherapy will be assessed prior to the procedure including: Basic Metabolic panel, CBC, Glomerular Filtration Rate, Coagulation Screen, and Urinalysis. Any abnormal labs will be reviewed by the Urologist and/or the Radiation Oncologist to determine clinical significance and the possible need for a reasonable delays or cancellation of the procedure. Any abnormal laboratory values will be repeated prior to proceeding with the procedure in such an event.

9.2 Effectiveness Assessments

Effectiveness will be analyzed by the rate of urinary obstruction beyond 7 days or infection directly related to the procedure, in addition to the analysis for the correlation of the biopsy samples with preoperative MR imaging. Statistical analysis of effectiveness is not anticipated due to the limited number of subjects in this exploratory initial analysis.

9.3 Other Response Parameters

The dose to the targeted lesion will be planned to be 150% of the prescribed peripheral dose to the prostate gland. The post-operative dosimetry and intraoperative dosimetry values will be recorded. In addition we will report the biopsy results for each targeted lesion to confirm correlation of the imaging with histopathology. There however will not be any therapeutic treatment alteration to be made based on the results for this study.

10.0 Statistical Plan

10.1 Sample Size Determination

Sample size justification: This is a hypothesis-generating pilot study with enrollment of 6 patients. Each patient is expected to have 12 to 15 tissue samples using standard sextant biopsies in addition to targeted biopsies of intraprostatic MRI findings. Assuming 14 specimens are sent for histopathology analysis in 6 subjects we will use the 84 biopsy sites. Based on the report in the literature [6], we expect the cancer lesion detection rate of 22% using multiparametric MRI/US fusion vs. 11% under current standard care. Ignoring the potential correlation of multiple lesions from the same patient, 6 patients (84 lesions) will have 82% power to detect in 11% improvement of detection rate using 2-sided one-sample chi-square test with a significance level of 0.05.

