1.4 Clinical Data to Date

The NCI went on to complete a human trial using the electromagnetic guidance system to compare MRI directed biopsies versus routine sextant biopsies in a series of 101 patients with a known diagnosis of prostate cancer. The data confirmed the transrectal ultrasound guided biopsy of the fused ultrasound and MR images yielded a higher rate of positive biopsies and also increased the yield for positive biopsies of high Gleason grade disease than routine ultrasound imaging directed biopsy alone (6). Limitations for the transrectal system include difficulty in placement of biopsy needles into regions seen in the anterior gland or transitional zone, as well as the increasingly prevalent risk of post procedural infections or rectal bleeding presumably related to the transrectal needle placement (9, 10).

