3.0 Study Design

3.1 General Design

This 1-year pilot study will include 6 patients with a clinical diagnosis of prostate cancer (clinical stage T2a or T1cN0M0), Gleason score ≤ 7 (4+3), with a PSA ≤ 15 ng/mL and routine pelvic screening with MRI of the prostate and pelvis for staging and treatment planning who have elected to undergo prostate brachytherapy as definitive treatment.

Only patients who have clinically detectable intraprostatic findings on the MRI will be eligible to participate, and will be screened from the routine population of patients undergoing prostate brachytherapy at University Hospitals.

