3.2 Primary Study Endpoints

The primary endpoint will be to report correlation of biopsy tissue histopathology with intraprostatic MRI findings. A total of 12 to 15 tissue samples will be obtained from each subject using standard sextant biopsies in addition to targeted biopsies of intraprostatic MRI findings. Assuming 14 specimens are sent for histopathology analysis in 6 subjects we will use the 84 biopsy sites to report sensitivity and specificity for the MRI findings along with positive and negative predictive values.

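### The detection-rate test behind the sample size (10.1) pools sextant and targeted cores against an external 11%, so it cannot credit MRI targeting and does not have 82% power for the effect expected

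*Combined protocol and SAP*

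**What the plan says.** Section 10.1 cites one published series (reference 6) for its rates: "we expect the cancer lesion detection rate of 22% using multiparametric MRI/US fusion vs. 11% under current standard care". It then states that "6 patients (84 lesions) will have 82% power to detect in 11% improvement of detection rate using 2-sided one-sample chi-square test" at a significance level of 0.05, setting aside correlation between samples from the same man. The 84 is 14 specimens in each of 6 men.

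Those specimens are of two kinds. Section 3.2, repeated in 10.1, has every man biopsied "using standard sextant biopsies in addition to targeted biopsies of intraprostatic MRI findings". The split between the two kinds is not given; only a total of 12 to 15 per man is.

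Section 1.4 describes the cited series as a trial run to "compare MRI directed biopsies versus routine sextant biopsies in a series of 101 patients", all with known prostate cancer, with fusion biopsy by the transrectal route. In the present trial biopsy is transperineal (6.1). Enrolment requires confirmed cancer within Gleason, stage and PSA limits (4.3.1), and section 3.1 adds: "Only patients who have clinically detectable intraprostatic findings on the MRI will be eligible to participate".

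Section 10.2 plans sensitivity, specificity and predictive values of MRI against histopathology, plus infection and hospitalization rates set against transrectal biopsy. It contains neither the test against 11% nor any targeted-versus-sextant contrast. Section 9.2 does not anticipate statistical analysis of effectiveness.

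**The concern.** There are two problems with the one detection-rate comparison in the plan.

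The first is the comparator. The 11% belongs to other men, biopsied by another route, and it is treated as a known constant. A one-sample test against it asks whether these 84 cores are positive more often than 11%. It does not ask whether targeting finds more cancer than sextant sampling. If the enrolled men simply have more cancer reachable by any core, the test responds in the same way. Each man supplies his own standard-care sample in the same gland on the same day, but the plan does not use it as the comparator.

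The second is pooling. The sextant cores, which stand for standard care, are counted among the 84 as though they carried the 22% rate. If they behave as standard care is expected to behave, they pull the pooled rate back towards 11%.

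At stake are the meaning of the 82% and how a rate above 11% would be read in the report anticipated in section 17.0.

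**Working it through.** **Inputs.** From 10.1: null rate p0 = 0.11, alternative p1 = 0.22, n = 14 × 6 = 84, two-sided 0.05, cores independent. Assumed because the documents do not give them: the sextant + targeted split per man, varied from 12+2 to 6+8 of 14; and the true core positivity in these men.

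**1. The plan's own figure.** Power = Φ[(p1 − p0 − 1.96·√(p0(1−p0)/n)) / √(p1(1−p1)/n)].
- √(0.11 × 0.89/84) = 0.0341, and 1.96 × 0.0341 = 0.0669.
- √(0.22 × 0.78/84) = 0.0452.
- Φ[(0.11 − 0.0669)/0.0452] = Φ(0.953) = 83.0%.

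This is within about a point of the stated 82%. Exact enumeration of the same chi-square rule gives 85.4%. So the arithmetic reproduces, provided all 84 cores are positive at 22%.

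**2. The rejection rule.** The expected count is 84 × 0.11 = 9.24 and the variance is 9.24 × 0.89 = 8.22. At 14 positive cores chi-square is 4.76²/8.22 = 2.76; at 15 it is 5.76²/8.22 = 4.03, above 3.84. The test rejects upward at 15 or more of 84 (17.9%).

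**3. No targeting effect, one common rate.** P(X ≥ 15) for X ~ Binomial(84, p):

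| Common positivity (assumed, except 11%) | Chance of rejecting upward |
|---|---|
| 11% | 4% |
| 15% | 27% |
| 20% | 73% |
| 25% | 95% |

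**4. The plan's expected effect, by core type.** Sextant cores at 11% and targeted cores at 22%, with s sextant and t targeted cores per man. Pooled rate = (0.11s + 0.22t)/14. Power is the exact chance that Binomial(6s, 0.11) + Binomial(6t, 0.22) falls in the rejection region. The last column is the targeted positivity needed for a pooled 22%: (0.22 × 14 − 0.11s)/t.

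| Split | Pooled rate | Power | Targeted rate needed |
|---|---|---|---|
| 12+2 | 12.6% | 10% | 88% |
| 11+3 | 13.4% | 15% | 62% |
| 10+4 | 14.1% | 20% | 50% |
| 8+6 | 15.7% | 34% | 37% |
| 6+8 | 17.3% | 49% | 30% |

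**5. What a within-man contrast can offer.** At 11% and 22% the standard error of the difference is √(0.11 × 0.89/(6s) + 0.22 × 0.78/(6t)). For 12+2 this is √(0.0979/72 + 0.1716/12) = 0.125, a 95% half-width of about 25 points. For 6+8 it is √(0.0979/36 + 0.1716/48) = 0.079, about 16 points. The expected difference is 11 points, so this is description, not a test.

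A sign-flip test over six men does not rescue it. By simulation at 11% versus 22% (40,000 runs, independent cores), its power in the right direction is below 1% at 12+2 and peaks at about 10% at 8+6. Unequal core counts also make its null distribution asymmetric: at 12+2 and a common 15%, it makes false claims in about 6% of trials, almost all saying that targeting is worse.

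**The case against.** The strongest reply is that nobody has committed to running this test. It appears only in 10.1, as justification for the number of men. Section 10.2 plans estimation, 9.2 does not anticipate statistical analysis of effectiveness, 10.1 calls the study hypothesis-generating, and 3.3.2 defines success by completed biopsies and infections. This stands. The probabilities in step 3 describe a claim that could be made, not one that the plan schedules. The power statement nevertheless remains in the protocol and attaches to an effect that no section estimates.

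A second reply is that targeted versus sextant is not the trial's question; the primary endpoint is agreement of MRI with histopathology. This stands in part. It is a reason to reword 10.1, but it does not make 82% a description of what the data can show.

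A third is that 6.1 has samples taken under MRI fusion, so the 22% might be meant for every core. Section 10.1 does not say so. The series it cites compared MRI-directed with sextant biopsies, and here the sextant cores play the standard-care part. Even on that reading the comparator remains external.

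A reader might also infer three stronger things that the documents do not support:
- That this is the plan's only comparison. Section 10.2 also compares infection or hospitalization with transrectal biopsy.
- That the sextant cores are ignored. They are among the 84 sites and feed the accuracy estimates; only their use as comparator is missing.
- That case mix is known to differ from the cited series. Both groups have known cancer. Apart from the biopsy route, the documents do not give enough about the cited series to show a difference. Case mix is uncontrolled, not shown to differ.

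**Conclusion.** The concern holds in limited form. The only detection-rate comparison in the plan pools both kinds of core and sets them against an external constant. It could signal improvement when targeting adds nothing (27% at a common 15%, 73% at a common 20%). It would usually miss the effect that the plan itself expects (power about 10% to 49%). These figures rest on independent cores, as 10.1 assumes, and on the assumed splits and common rates; the documents fix neither. The stated 82% is arithmetically sound for 84 cores all positive at 22%, so it is not a calculation error. The damage is to the sizing rationale and to the reading of any rate above 11%. It does not reach the accuracy estimates or the safety endpoints. The change is worth making because the data for it are already collected.

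**What to change.** In 10.1, describe the study as estimation in six men and keep 11% and 22% as background from the cited series. Either withdraw the 82% power statement or say that it does not support a conclusion about targeting.

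In 10.2, add that targeted and sextant positivity will be reported separately for each man, with core counts, the six within-man differences (targeted minus sextant) and their mean. Present these descriptively, without a sign-flip p-value.

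The cost is a wording change in two sections and one extra table, with no additional cores or patients. The downside is an imprecise contrast that rests on six men, and the report should say so.

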4.2 Anticipated Number of Research Subjects

The pilot study is designed to include only 6 subjects for testing of feasibility to obtain transperineal tissues and report correlation to MRI image findings.

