6.0 Study Biopsy Procedures

6.1 Description biopsy procedure

All biopsies will be completed in the outpatient setting in the ambulatory OR prior to routine prostate brachytherapy under general anesthesia. Patients will be prepped in a dorsal lithotomy position with insertion of a Foley catheter. The perineum will be shaved as needed, and cleansed with antiseptic solution, and the scrotum will be elevated with a towel roll to expose the perineum. The FDA approved DynaCAD and Uronav system will be used to localize the diagnostic MRI findings within the prostate. The 510K approved tranperineal Uronav system will

be used to perform transperineal biopsy with electromagnetic alignment of the transrectal probe and stepper system attached to the perineal biopsy guide 17 gauge template.

Specimens will be sent to anatomic pathology office of:
[name] in separate cassettes at [name]
[name]
[name]

They will be received by [name], PhD.

Each specimen will be sent separately and identified by location in the prostate (1-12 a or p to identify the involved portion of the gland divided in 12 sextants and either anterior or posterior to midline of the coronal plane) along with PIRADS classification of the lesion in MRI report. The proximal and distal end of the sample will be dyed for orientation in the OR at the time of acquisition of each sample, or at a minimum noted if it is from the proximal, mid or distal 1/3 portion of the biopsy cavity to correlate with the same region of the virtual fiducial marker placed at the site of the biopsy.

Standard stains will be used to identify tumors within the specimen with photos taken after processing is completed to allow localization relative to the virtual fiducial marker placed at the site of the biopsy using the Uronav system. The pathology evaluation will be provided through [name].

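### The 82% power in 10.1 treats all 84 biopsy sites, sextant cores included, as lesions at the 22% fusion rate, and the test behind it is not in the planned analysis

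*Combined protocol and SAP*

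**What the plan says.** Section 10.1 calls the study a hypothesis-generating pilot of 6 patients. On the material collected it says: "Each patient is expected to have 12 to 15 tissue samples using standard sextant biopsies in addition to targeted biopsies of intraprostatic MRI findings". It assumes 14 specimens per man, which gives 84 biopsy sites. From a literature report it takes the rates: "we expect the cancer lesion detection rate of 22% using multiparametric MRI/US fusion vs. 11% under current standard care". It then concludes that "6 patients (84 lesions) will have 82% power to detect in 11% improvement of detection rate", using a two-sided one-sample chi-square test at the 0.05 level, and says openly that correlation between lesions in one patient is ignored.

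Other sections bear on this:

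- Section 3.2 confirms that 12 to 15 is the total per man ("A total of 12 to 15 tissue samples will be obtained from each subject using standard sextant biopsies in addition to targeted biopsies") and gives the purpose of the sites: "we will use the 84 biopsy sites to report sensitivity and specificity for the MRI findings", together with the predictive values.
- Section 1.4 describes the cited study as one "to compare MRI directed biopsies versus routine sextant biopsies in a series of 101 patients with a known diagnosis of prostate cancer".
- Section 6.1 labels specimens by location, "to identify the involved portion of the gland divided in 12 sextants".
- Section 10.2 plans binomial estimates of sensitivity, specificity, PPV and NPV. Its only comparison concerns infection or hospitalization.
- Section 9.2 does not anticipate a statistical analysis of effectiveness, because there are so few subjects.
- Section 4.2 describes the pilot as "designed to include only 6 subjects for testing of feasibility to obtain transperineal tissues".

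**The concern.** Within section 10.1 the unit changes from biopsy sites to lesions. The sites are a mixture of sextant and targeted cores. Section 3.2 uses the same sites for specificity, which requires sites that are negative on MRI, so they cannot all be MRI lesions. Eligibility asks for at least one suspicious region (section 4.1), and nothing in the plan supports 14 lesions per man.

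The unit matters because the alternative rate of 22% is tied to MRI/US fusion. If that rate belongs to targeted cores only, applying it to the sextant cores inflates either the number of informative units or the expected overall rate.

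The test that is powered also appears nowhere except in the power sentence. One section says the numbers are too small for statistical analysis of effectiveness, and another offers 82% power. An IRB member or reader would take it that the pilot has good power for a detection contrast that it does not plan to test. Nothing is said about the precision of the estimates it does plan to report.

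**Working it through.** **Inputs.** From section 10.1: p0 = 0.11, p1 = 0.22, two-sided alpha 0.05, n = 14 × 6 = 84, cores independent. The number of targeted cores per man, k, is not given. Two readings of sextant bound it at 14 cores per man:

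- 12 systematic cores (the 12 regions in sections 1.2 and 6.1): k = 14 − 12 = 2.
- 6 systematic cores: k = 14 − 6 = 8, or 15 − 6 = 9 at the upper core count.

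**Formula.** With s0 = √(p0(1−p0)/n) and s1 = √(p1(1−p1)/n), power = Φ[(p1 − p0 − 1.96·s0)/s1], plus the lower-tail term Φ[(−(p1 − p0) − 1.96·s0)/s1], which is below 1 percentage point in step 2 and at most about 1 point in step 3.

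**Step 1. The plan's own figure.** At n = 84, s0 = 0.03414 and s1 = 0.04520. Then (0.11 − 0.06691)/0.04520 = 0.953 and Φ(0.953) = 83.0%. The stated 82% is reproduced to within about one point, but only with all 84 sites at 22%.

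**Step 2. Targeted cores only, with 22% as the targeted-core rate.**

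| Targeted cores per man | n | Power |
|---|---|---|
| 2 | 12 | 29.6% |
| 4 | 24 | about 43% |
| 8 | 48 | 64.1% |
| 9 (of 15) | 54 | 68.1% |

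Reaching 82% takes about 81 to 82 targeted cores (81.9% at 81, 82.2% at 82), which is nearly every core in the study.

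**Step 3. All 84 cores tested together, targeted at 22% and sextant at an assumed 11%** (the plan's standard-care rate). The overall rate is [0.22k + 0.11(14 − k)]/14.

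| k of 14 | Overall rate | Power at n = 84 |
|---|---|---|
| 2 | 12.6% | 9.0% |
| 4 | 14.1% | 18.0% |
| 8 | 17.3% | 46.2% |

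**Step 4. What would make 22% overall true.** With sextant cores at 11%, the targeted rate must be t = [14 × 0.22 − (14 − k) × 0.11]/k. This gives 88.0% for k = 2, 49.5% for k = 4, 36.7% for k = 6 and 30.3% for k = 8. Other mixes also work: 4 cores at 40% and 10 at 14.8% average 22%. The plan states none of these rates.

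**Step 5. Link to the analysis.** Section 10.2 estimates diagnostic-accuracy proportions and contains no test of a detection rate against 11%. Its one comparison, with transrectal biopsy, is on infection or hospitalization. This step needs no assumption about what the 22% means.

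**The case against.** The strongest reply is that section 10.1 does not call 22% a per-core rate for targeted biopsies, and the cited report cannot be checked from the documents. Section 6.1 describes the biopsy samples generally as taken with ultrasound fused to the MRI, so 22% could be meant as the yield of the whole fusion-guided procedure. On that reading 84 is the right denominator. Step 4 shows it is attainable: 8 targeted cores at 30% and the rest at 11% give an overall 21.9% and 82% power. This stands as far as it goes, and it is why the lower power figures are conditional. It does not rescue the label of 84 lesions, and the targeted-core rate it needs is nowhere stated.

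The case of 2 targeted cores per man is also an extreme. Section 6.1 uses the 12 regions as location labels and does not give a core count. Twelve systematic cores would leave no targeted core at the lower limit of 12 samples, although every eligible man has an MRI finding. Six sextant cores avoid that problem and give the smaller gap of 64% to 68% on targeted cores. Two per man is best read as one end of the range, since sections 1.2 and 6.1 both describe 12 regions.

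Finally, the plan labels itself hypothesis-generating and discloses that correlation is ignored. Its success criterion (section 3.3.2) and stopping rules (sections 10.3 and 11.8) do not use the 82%. That is correct and limits the consequence.

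**Conclusion.** The point holds. The arithmetic is sound for its inputs, but the unit of 84 lesions contradicts the make-up of the 84 sites given in the same section, and the powered test is not part of the planned analysis. Both conclusions rest on the documents alone.

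The size is conditional. If 22% is the targeted-core rate and cores are independent, power is about 30% to 68% on 12 to 54 targeted cores. With all 84 cores pooled, sextant cores at 11% and 2 to 8 targeted cores per man, it is about 9% to 46%. If 22% is an overall rate, the 82% can stand, but only with a targeted-core rate well above 22% (about 30% to 88% with sextant cores at 11%).

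The fault is a misleading sample-size statement. It does not make a planned analysis wrong and changes no decision in the study, and the disclosed neglect of within-patient correlation is not part of it. It should be fixed, because the figure supports a claim the design does not make good.

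**What to change.** In section 10.1:

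- Delete the 82% power statement and the term 84 lesions, or restate power on the planned number of targeted cores with the assumed rate for each core type. If a powered test is kept, add the same test to section 10.2 and reconcile it with section 9.2.
- State the planned numbers of targeted and systematic cores per patient.
- Rest the 6 patients on the feasibility aim already in section 4.2.

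It would also help, though it is optional, to give the expected precision of sensitivity, specificity, PPV and NPV as exact or Wilson 95% intervals over stated assumed counts. For illustration only, with counts that are not in the plan, a sensitivity of 7/9 has a Wilson interval of about 45% to 94%, and 15/18 about 61% to 94%. Such intervals ignore clustering within 6 men and are therefore likely too narrow.

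The cost is rewording, in section 10.1 alone if the claim is deleted. No patients, cores or procedures are added. The only downside is a less favourable figure, or none.
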